Adverse events (AEs) will be coded using the Medical Dictionary for Regulatory Activities (MedDRA). The number and percentage of subjects with treatment-emergent AEs, serious AEs (SAEs), AEs leading to withdrawal of treatment, and AEs possibly related to the study drug will be calculated. Changes in laboratory parameters, vital signs, and weight over time will be tabulated. **Efficacy:**

The PSA response rate will be summarized by time point.

Pharmacokinetics:

Not applicable

Pharmacodynamics:

Not applicable

Interim analyses:

An interim assessment will be conducted at 6 month from first subject enrollment, with respect to safety. The report will be submitted to the health authority.

V. FLOW CHART AND SCHEDULE OF ASSESSMENTS

Flow Chart

Study Day	Screening Visit	1	29	57	85	169 & every subsequent 84 days	Safety Follow-up	Unscheduled
Study Week	-4 to -1 (28 Days)	1	5	9	13	25	30 Days after Last Dose§	Visit†
Window (Days)			± 7	± 7	± 7	± 7	± 7	NA
Informed Consent	Х							
Medical History	Х							
Inclusion/Exclusion Criteria	Х	Х						
IRT		Х						
Vital Signs	Х	Х	Х	Х	Х	Х	Х	Х
Physical Examination including Weight¶	Х	Х	Х	Х	Х	Х	Х	Х
Height	Х							
Clinical Labs ‡	Х	Х	Х	Х	Х	Х	Х	Х
PSA	Х	Х	Х	Х	X	Х	Х	
ECOG Performance Status	Х							
Adverse Events§§	Х	Х	Х	X	X	Х	Х	Х
Previous and Concomitant Medications	X	Х	Х	Х	Х	X	Х	Х
Study Drug Dispensing		Х	Х	Х	X	Х		
Study Drug Treatment		Х	Х	X	Х	Х		

Table 1: Schedule of Assessments

ECOG: Eastern Cooperative Oncology Group; IRT: Interactive Response Technology; NA: not applicable; PSA: prostate-specific antigen

- [†] Unscheduled visits may be performed at any time during the study whenever necessary to assess for or follow-up on adverse events at the subject's request or if deemed necessary by the Investigator. Procedures and assessments are to be performed as clinically indicated.
- § Or prior to initiation of an investigational agent or new therapy for prostate cancer, whichever occurs first.
- A brief physical examination is required at each visit, with the exception of the screening visit during which a complete physical examination will be completed.
- ‡ Laboratory assessments include serum chemistries and hematology.

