6 DISCONTINUATION

6.1 **Discontinuation of Individual Subject(s)**

The subject is free to withdraw from the study treatment and/or study for any reason and at any time without giving reason for doing so and without penalty or prejudice. The Investigator is also free to terminate a subject's involvement in the study at any time if the subject's clinical condition warrants it.

Discontinuation Criteria from Study Drug Treatment for Individual Subjects:

- Any AE that is intolerable to the subject which cannot be ameliorated by the use of adequate medical intervention and/or dose reduction or that in the opinion of the Investigator would lead to undue risk to the subject if dosing is continued.
- Subject who experiences a seizure or any condition that significantly predisposes the subject to seizure such as brain metastasis or clinically evident stroke.
- Subject who experiences a confirmed event of PRES by brain imaging, preferably by MRI.
- Subject initiates an investigational agent or new therapy for prostate cancer.
- Subject who has evidence of radiological disease progression and/or PSA progression as confirmed by the Investigator and is no longer deriving clinical benefit. Imaging test can be done at the discretion of the investigator and are not part of the study.
- Subject has discontinued ADT (GnRH agonist/antagonist) and has a testosterone value in the noncastrate range (> 50 ng/dL).
- Subject who is, in the opinion of the Investigator or the Medical Monitor, non-compliant with the protocol requirements.
- Subject is lost to follow-up despite reasonable efforts by the Investigator to locate the subject.
- Subject withdraws consent for the study.

Subject will be discontinued from the 30 day study follow-up (Safety or Long-term Follow-up) if any of the following occur:

- Subject is lost to follow-up despite reasonable efforts by the Investigator to locate the subject.
- Subject withdraws consent for further follow-up.
- Death.
- Study termination by the Sponsor.

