ECOG	Eastern Cooperative Oncology Group	
FAS	Full Analysis Set	
Hb	Hemoglobin	
HLGT	High Level Group Term	
HLT	High Level Term	
ICH	International Council for Harmonisation	
IHD	Ischemic Heart Disease	
ISN	International Study Number	
mCRPC	Metastatic Castration-Resistant Prostate Cancer	
MedDRA	Medical Dictionary for Regulatory Activities	
NA	Not Applicable	
NCI	National Cancer Institute	
PD	Pharmacodynamics	
РК	Pharmacokinetics	
PRES	Posterior Reversible Encephalopathy Syndrome	
PSA	Prostate-Specific Antigen	
РТ	Preferred Term	
SAF	Safety Analysis Set	
SAP	Statistical Analysis Plan	
SCAR	Severe Cutaneous Adverse Reactions	
SD	Standard Deviation	
SMQ	Standardized MedDRA Queries	
SOC	System Organ Class	
SPM	Second Primary Malignancies	
TEAE	Treatment Emergent Adverse Event	
TLFs	Tables, Listings, and Figures	
ULN	Upper limit of normal	
WHO	World Health Organization	
WHODDE(B2)	WHO Drug Dictionary Enhanced (B-2 Format)	

List of Key Terms

Terms	Definition of terms
Baseline	Assessments of subjects as they enter a trial before they receive any treatment.
Endpoint	Variable that pertains to the efficacy or safety evaluations of a trial.
Enroll	To register or enter a subject into a clinical trial. NOTE: Once a subject has received the study drug or placebo, the clinical trial protocol applies to the subject.
Investigational period	Period of time where major interests of protocol objectives are observed, and where the test drug or comparative drug (sometimes without randomization) is usually given to a subject, and continues until the last assessment after completing administration of the test drug or comparative drug.
Post investigational period	Period of time after the last assessment of the protocol. Follow-up observations for sustained adverse events and/or survival are done in this period.
Screening	A process of active consideration of potential subjects for enrollment in a trial.
Screen failure	Potential subject who did not meet 1 or more criteria required for participation in a trial.
Screening period	Period of time before entering the investigational period, usually from the time when a subject signs the consent until just before the test drug or comparative drug (sometimes without randomization) is given to a subject.
Study period	Period of time from the first site initiation date to the last site completing the study.
Variable	Any entity that varies; any attribute, phenomenon or event that can have different qualitative or quantitative values.

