7.4 Analysis of Efficacy

Efficacy analysis will be conducted on the FAS.

PSA response rate (the proportion of patients with $\geq 50\%$ decline in PSA from baseline) will be summarized at each visit (See Section 7.11.3).

Confirmed PSA response rate (the proportion of patients with $\geq 50\%$ decline in PSA from baseline to the lowest postbaseline PSA result, with a consecutive assessment conducted at least 3 weeks later to confirm the PSA response) will be summarized.

Summary statistics of measured values and the percent changes from baseline will be calculated at each visit and mean \pm standard deviation (SD) plots will be constructed.

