7.5.2.2 Liver Enzymes and Total Bilirubin

The following potentially clinically significant criteria for liver tests – defined as Alkaline Phosphatase (ALP), Alanine Transaminase (ALT), total bilirubin, Aspartate Transaminase (AST) and their combination are defined. The subject's highest value during the study period will be used.

Parameter	Criteria
ALT	> 3xULN
	> 5xULN
	> 10xULN
	>20xULN
AST	> 3xULN
	> 5xULN
	> 10xULN
	>20xULN
ALT or AST	> 3xULN
	> 5xULN
	> 10xULN
	>20xULN
Total Bilirubin	>2xULN
Alkaline Phosphatase	> 1.5xULN
ALT and/or AST AND Total Bilirubin [1]	ALT and/or AST > 3xULN AND Total Bilirubin > 2xULN
ALT and/or AST AND Alkaline Phosphatase AND Total Bilirubin [1]	ALT and/or AST > 3xULN AND Alkaline Phosphatase < 2xULN AND Total Bilirubin > 2xULN

[1] Combination of values measured within same day or within 1 day apart

The number and percentage of subjects with potentially clinically significant values in liver enzyme and total bilirubin tests during the study period will be presented.

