7.11.2 Outliers

All values will be included in the analyses.

	ior vitai Signs, Chincai La	
Analysis visit	Specified day	Allowed time window
Baseline	Day0001	Last nonmissing value before the first dose.
Day0029(Week5)	Day0029	Specified day \pm 7 days
Day0057(Week9)	Day0057	Specified day \pm 7 days
Day0085(Week13)	Day0085	Specified day \pm 7 days
Day0169(Week25)	Day0169	Specified day \pm 7 days
Day0253(Week37)	Day0253	Specified day \pm 7 days
Day0337(Week49)	Day0337	Specified day \pm 7 days
Day0421(Week61)	Day0421	Specified day \pm 7 days
Day0505(Week73)	Day0505	Specified day \pm 7 days
Day0589(Week85)	Day0589	Specified day \pm 7 days
Day0673(Week97)	Day0673	Specified day \pm 7 days
Day0757(Week109)	Day0757	Specified day \pm 7 days
Day0841(Week121)	Day0841	Specified day \pm 7 days
Day0925(Week133)	Day0925	Specified day \pm 7 days
Day1009(Week145)	Day1009	Specified day \pm 7 days
Day1093(Week157)	Day1093	Specified day \pm 7 days
Day1177(Week169)	Day1177	Specified day \pm 7 days
Day1261(Week181)	Day1261	Specified day \pm 7 days
Day1345(Week193)	Day1345	Specified day \pm 7 days
Day1429(Week205)	Day1429	Specified day \pm 7 days
Safety Follow-up	30 days after Last Dose	Specified day \pm 7 days

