7.11.3 Visit Window for Vital Signs, Clinical Labs and PSA

As for the analysis visits of Day XXXX (Week XXX), the values measured on or before withdrawal day will be accepted for discontinued subjects. The value which assessment day is the closest to the defined specified day within this window is used. If two values are equally close, the latter is used in the analysis.

Version	Date	Changes	Comment/rationale for change
1.0	3-Jun-2019	NA	Document finalized
2.0	25-Jan-2021	Protocol DeviationsTo include the analysis of protocol deviations according to the change quality documents.	
3.0	26-Feb-2024	GeneralConsiderationsRemoved dictionaryversion of MedDRA andWHODDE.	To comply with the Statistical Analysis Plan template.
		Visit Window for Vital Signs, Clinical Labs and PSA Updated time windows for visit increase.	To address visit increase.
		Missing Data Updated imputation for partial missing start/end dates of AE, CM, MH, PR.	To address partial missing dates.
		FLOW CHART AND VISIT SCHEDULE Removed the flow chart and visit schedule and changed to refer to the protocol.	To follow the contents of latest Statistical Analysis Plan format.
		General Considerations Updated SAS version.	

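### The confirmed PSA response has no cut-off at new prostate cancer therapy, and the liver maximum runs over a trial-wide period that, read literally, includes pre-dose values

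*SAP*

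**What the plan says.** **PSA.** SAP 6.1 and 7.4 define confirmed response as a fall of at least half from baseline to the lowest later value, "with a consecutive assessment conducted at least 3 weeks later to confirm the PSA response". Neither section gives a last eligible date, whether last dose, withdrawal or start of another therapy. SAP 7.4 refers to the visit windows of 7.11.3 for the by-visit response rate only. Under those windows "the values measured on or before withdrawal day will be accepted for discontinued subjects", but that sentence is confined to the numbered Day visits. The Safety Follow-up row, "30 days after Last Dose" with 7 days either side, carries no such limit.

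**New therapy.** The Protocol Table 1 footnote times the follow-up visit as "Or prior to initiation of an investigational agent or new therapy for prostate cancer, whichever occurs first", and Protocol 2.2.1 and SAP 3.2 agree. Protocol 6.1 lists among the reasons to stop study drug: "Subject initiates an investigational agent or new therapy for prostate cancer".

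**Liver.** For the liver criteria in SAP 7.5.2.2, each subject's "highest value during the study period will be used". The SAP key terms define study period as "Period of time from the first site initiation date to the last site completing the study".

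**The concern.** Once a subject has started another prostate cancer drug, a PSA value no longer measures enzalutamide alone. The confirmed rate is meant to describe the effect of enzalutamide on PSA, and nothing in its definition keeps such a value out.

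The liver rule has a different problem. The potentially clinically significant counts are part of the primary safety evaluation. A period that opens at first site initiation has already opened when every subject is screened. A transaminase raised at screening and normal from the first dose onward would then be counted as if it had arisen on treatment.

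**Working it through.** The plan gives no power, alpha or event figure to reproduce, since SAP 4 says the sample size is not power-based. The check is a reading of the rules plus simple arithmetic.

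1. **Is there any PSA cut-off?** SAP 6.1 and 7.4 have none. The withdrawal-day rule in 7.11.3 covers the numbered visits, is tied to withdrawal rather than to new therapy, and is not invoked for the confirmed rate. The follow-up row has none. Deviation code PD4 (excluded concomitant treatment, Protocol 8.1.6 and SAP 7.2.2) reports a subject but removes no value.

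2. **Can a follow-up PSA act as confirmer?** Its window is 30 − 7 = 23 to 30 + 7 = 37 days after last dose. Confirmation needs 3 × 7 = 21 days after the earlier PSA.
   - If the earlier PSA was taken by about the last dose, the gap is at least about 23 days and the rule is met.
   - If not, it can fail. With last dose on Day 166, PSA on Day 169 and follow-up on Day 166 + 23 = 189, the gap is 189 − 169 = 20 days.

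3. **When does it matter most?** Scheduled PSAs are 169 − 85 = 84 and 253 − 169 = 84 days apart. For a decline first seen at Day 169 in a subject who stops before Day 253, the follow-up sample is the only scheduled confirmer.

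4. **Direction.**
   - A post-switch value that stays low can confirm an earlier on-drug decline, which adds a response.
   - A post-switch value that is the lowest of all becomes the nadir. No later scheduled sample exists to confirm it, so a literal reading can lose a response that earlier on-drug values would have supported.

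5. **Weight of one subject.** 1/50 = 2.0 percentage points, or 1/40 = 2.5 if the full analysis set were 40 (assumed). If 1 to 5 subjects were affected (assumed), and all in the same direction, the shift is 2 to 10 points. For scale, exact 95% intervals from an assumed 25 responders:

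| Responders | Rate | 95% CI |
|---|---|---|
| 25/50 | 50% | 35.5% to 64.5% |
| 26/50 | 52% | 37.4% to 66.3% |
| 30/50 | 60% | 45.2% to 73.6% |

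6. **Liver window.** Protocol Table 1 marks clinical labs at screening and Day 1. SAP 7.11.3 treats the last value before first dose as baseline. Both visits lie inside a period bounded by first and last site dates. Protocol 3.2 and 3.3 state no transaminase limit of their own; they defer to the local prescribing information, which is not in the documents. One such subject turns 0/50 (exact upper limit 7.1%) into 1/50 (2%, 0.1% to 10.6%).

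7. **Should post-switch liver values be dropped?** No. With the mean half-life of 5.8 days in Protocol 1.2.2, the fraction of drug remaining is 0.5^(t/5.8): 43.3% at 7 days, 18.8% at 14, 6.4% at 23 and 1.2% at 37. Early values after stopping can still reflect enzalutamide.

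8. **Partial start dates.** SAP 7.11.1 sets an unknown start day to the 1st and an unknown month to January. A true 31st becomes the 1st, 30 days early. A true 31 December becomes 1 January, 364 days early (365 in a leap year). If a cut-off used such a date unguarded, it would delete valid on-drug PSA values.

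**The case against.** The strongest reply is that the PSA case requires a departure from the planned order. Follow-up is due before any new therapy, antitumour agents are prohibited during treatment, and Table 1 does not mark PSA at unscheduled visits. A late follow-up sample is therefore the main route. That stands, and it is why the effect is small. It does not close the gap: the footnote instructs sites when to hold a visit and does not tell the analyst what to do with a value, and Protocol 6.1 foresees the subject who switches first.

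On the liver side, SAP 7.2.1 uses study period in a subject-level sense, set against the screening period, so a programmer might exclude screening values anyway. That shows the term is ambiguous; the formal definition still says otherwise. The table specifications, which are not in the documents, might settle it.

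Four stronger readings are tempting, and the documents do not support them:

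- A reader might take "All values will be included in the analyses" as admitting post-switch PSA. It is the outlier rule in SAP 7.11.2 and concerns extreme values.
- A reader might blame the trial-wide period for the lack of any mark on post-switch liver values. A subject-level window ending at the follow-up visit would contain the same values unmarked. The period causes the pre-dose problem only.
- A reader might infer that the response rate is inflated. Step 4 of the working shows that the direction is not fixed.
- A reader might use the 42.0% of enzalutamide subjects with later therapies in the post-docetaxel phase 3 study (Protocol 1.4) as the number at risk. That figure carries no timing relative to a follow-up visit.

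**Conclusion.** Both points hold, and both are modest.

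The confirmed PSA definition lets a value taken on another drug act as nadir or confirmer when a subject switches before the follow-up sample. The number affected cannot be derived from the documents and is probably very small. Each misclassified subject is worth 2.0 points with 50 in the full analysis set. The trial is single-arm and descriptive with no hypothesis test, so no formal decision turns on this.

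The liver definition, read literally, counts pre-dose values. This needs no protocol departure. It affects only a subject whose screening or Day 1 value meets a criterion that no later value meets.

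The case for changing both is that the rules are specific, less biased and nearly free, and are best settled before results are seen.

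**What to change.** 1. **SAP 7.4 (and 6.1):** for the nadir and its confirmation, use only PSA values dated on or before the start of new prostate cancer therapy, and list the values left out. If the start date is partial, do not let the imputed date fall before the last dose unless the recorded parts show that it did. Say whether PSA on commercial enzalutamide, which Protocol 2.2.1 counts as new therapy, is kept.
2. **SAP 7.5.2.2:** replace study period with the interval from first dose to the safety follow-up visit, and keep every value in it.

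Marking post-switch liver values or follow-up-row values is optional.

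The cost is a few sentences and one listing. Protocol 5.1.3 already collects medications up to the final follow-up visit. The downside is that a few PSA values move from the analysis to a listing. The partial-date guard is needed only because the cut-off would otherwise rely on the imputation in SAP 7.11.1. If the SAP can no longer be amended, SAP 1 allows a change to be justified in the study report.

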7.5 Analysis of Safety

All analysis of safety will be presented for SAF, unless specified otherwise.

7.5.1 Adverse Events

Following definitions of AE will be used for analysis.

The definitions of TEAE and drug-related TEAE are provided in Section 6.2.

7.5.1.1 An Overview of Adverse Events

An overview table will include the following details:

- Number and percentage of subjects with TEAEs
- Number and percentage of subjects with drug-related TEAEs
- Number and percentage of subjects with serious TEAEs
- Number and percentage of subjects with drug-related serious TEAEs
- Number and percentage of subjects with TEAEs leading to death
- Number and percentage of subjects with drug-related TEAEs leading to death
- Number and percentage of subjects with TEAEs leading to withdrawal of treatment
- Number and percentage of subjects with drug-related TEAEs leading to withdrawal of treatment
- Number and percentage of subjects with grade 3 or higher TEAEs
- Number and percentage of subjects with drug-related grade 3 or higher TEAEs
- Number and percentage of subjects with deaths
- Number of TEAEss
- Number of drug-related TEAEs
- Number of serious TEAEs
- Number of drug-related serious TEAEs
- Number of TEAEs leading to death
- Number of drug-related TEAEs leading to death
- Number of TEAEs leading to withdrawal of treatment
- Number of drug-related TEAEs leading to withdrawal of treatment
- Number of grade 3 or higher TEAEs
- Number of drug-related grade 3 or higher TEAEs

7.5.1.2 Adverse Events by SOC and PT

The number and percentage of subjects with TEAEs and number of TEAEs, as classified by SOC and PT will be summarized. Subjects reporting more than one AE for a given MedDRA PT will be counted only once for that term. Subjects reporting more than one AE within a SOC will be counted only once for the SOC total. Subjects reporting more than one AE will be counted only once in the overall AE total.

For summaries by severity based on National Cancer Institute Common Terminology Criteria for Adverse Events (NCI-CTCAE) grade (Grade 1 = mild, Grade 2 = moderate, Grade 3 = severe or medically significant, Grade 4 = life threatening, Grade 5 = death related to AE), subjects reporting more than one AE for a given PT, SOC total and AE total will be counted only once for that term in the most severe category reported. If a subject has an AE which has a missing severity, then the subject will be counted in the severity category of "Missing" (i.e., missing severity will not be imputed).

Summaries will be provided for:

- TEAEs
- Drug-related TEAEs
- Serious TEAEs
- Drug-related serious TEAEs
- TEAEs leading to withdrawal of treatment
- Drug-related TEAEs leading to withdrawal of treatment
- TEAEs leading to death
- Drug-Related TEAEs leading to death
- Grade 3 or higher TEAEs
- Drug-related grade 3 or higher TEAEs
- Common (>=5%) TEAEs
- TEAEs by severity based on NCI-CTCAE grade
- Drug-related TEAEs by severity based on NCI-CTCAE grade
- Common (>=5%) TEAEs excluding serious adverse events

7.5.1.3 Adverse Events of Special Interest

An overview table of TEAE of Special Interest will describe the number and percentage of patients, as classified by AESI category and PT.

An overview table of TEAE of Special Interest with Grade 3 or above will describe the number and percentage of patients, as classified by AESI category and Severity.

7.5.2 Clinical Laboratory Evaluation

7.5.2.1 All Laboratory Tests

Descriptive statistics for quantitative clinical laboratory variables, i.e. hematology and biochemistry will be presented at each visit (See Section 7.11.3). Additionally, a withinsubject change will be calculated as the postbaseline measurement minus the baseline measurement and summarized in the same way. Each laboratory result will be classified as low (L), normal (N), or high (H) at each visit according to the laboratory supplied reference ranges. The number and percentage of subjects below and above reference range will be summarized using shift table (from baseline to postbaseline).

The following data will be presented for quantitative clinical laboratory variables graphically:

- Laboratory test results (actual values) using box plot
- Laboratory test results x study days (relative days from administration of the study drug) using spaghetti plot

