2.3 Endpoints

2.3.1 Primary Endpoints

Safety

- Nature, frequency and severity of adverse events
- Safety laboratory tests: biochemistry and hematology
- Physical examination
- Vital signs (blood pressure, pulse and temperature)

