5.5.1.1 Abnormal Laboratory Findings

Any abnormal laboratory test result (e.g. hematology, clinical chemistry, or urinalysis) or other safety assessment (e.g., ECGs, radiolographic scans, vital signs measurements, physical examination), including those that worsen from baseline, that is considered to be clinically significant in the medical and scientific judgment of the investigator and not related to underlying disease, is to be reported as an (S)AE.

Any clinically significant abnormal laboratory finding or other abnormal safety assessment which is associated with the underlying disease does not require reporting as an (S)AE, unless judged by the investigator to be more severe than expected for the subject's condition.

Repeating an abnormal laboratory test or other safety assessment, in the absence of any of the above criteria, does not constitute an AE. Any abnormal test result that is determined to be an error does not require reporting as an AE.

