5.5.4 Criteria for Defining the Severity of an Adverse Event

AEs, including abnormal clinical laboratory values, will be graded using the CTCAE guidelines (Version 4.03). The items that are not stipulated in the NCI-CTCAE Version 4.03 will be assessed according to the criteria below and entered into the eCRF.

Grade	Assessment Standard
1-Mild	Asymptomatic or mild symptoms, clinical or diagnostic observations noted; intervention not indicated.
2-Moderate	Local or noninvasive intervention indicated.
3-Severe	Medically significant but not immediately life threatening, hospitalization or prolonged hospitalization.
4-Life Threatening	Life threatening consequences, urgent intervention indicated
5-Death	Death related to AE

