7.5.2 Laboratory Assessments

For quantitative laboratory measurements descriptive statistics will be used to summarize results and change from baseline for subjects in the SAF.

Shifts relative to normal ranges from baseline to each time point during treatment period in lab tests will also be tabulated. Laboratory data will be displayed in listings.

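### Laboratory shift tables stop at low/normal/high, so no planned table counts Grade 3-4 haematology or non-liver chemistry values from the central-laboratory data

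*SAP*

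**What the plan says.** Protocol 2.3.1 lists "Safety laboratory tests: biochemistry and hematology" as a primary endpoint, separately from adverse events, and SAP 6.2 repeats this.

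On the laboratory analysis, protocol 7.5.2 says: "Shifts relative to normal ranges from baseline to each time point during treatment period in lab tests will also be tabulated". SAP 7.5.2.1 carries that out: "Each laboratory result will be classified as low (L), normal (N), or high (H) at each visit", using the laboratory's own reference ranges, and "The number and percentage of subjects below and above reference range will be summarized using shift table (from baseline to postbaseline"). The same SAP section adds by-visit descriptive statistics, change from baseline, box plots and spaghetti plots. Protocol 7.5.2 adds listings.

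Liver tests have their own table in SAP 7.5.2.2, based on each subject's highest value: ALT and AST at >3, >5, >10 and >20 x ULN, total bilirubin at >2 x ULN, ALP at >1.5 x ULN, and combinations.

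Severity grading appears under adverse events. Protocol 5.5.4 says: "AEs, including abnormal clinical laboratory values, will be graded using the CTCAE guidelines (Version 4.03"). SAP 7.5.1.2 plans "TEAEs by severity based on NCI-CTCAE grade" and a summary of events of Grade 3 or higher. SAP 7.5.1.3 plans a table of Grade 3 or higher events of special interest, whose categories in SAP 6.2 include decreased neutrophil count and thrombocytopenia.

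Protocol 5.5.1.1 decides which laboratory abnormalities become adverse events. A result is reported if it is one "that is considered to be clinically significant in the medical and scientific judgment of the investigator and not related to underlying disease". In contrast, "Any clinically significant abnormal laboratory finding or other abnormal safety assessment which is associated with the underlying disease does not require reporting" as an adverse event, except where the investigator judges it more severe than expected for that subject.

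**The concern.** A three-category shift shows whether a result crossed the edge of the reference range. It does not show how far. In men with metastatic disease who have already had docetaxel, some will plausibly start with low blood counts, and for them the edge has already been crossed. If their counts fall further, the shift table records no movement.

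The graded adverse-event tables would normally supply the severity, but an abnormality reaches them only after the investigator has judged it clinically significant and either unrelated to the disease or worse than expected. Attributing a cytopenia to the cancer is a foreseeable judgement here. At stake is whether the report can state, from the laboratory values themselves, how many subjects reached Grade 3 or 4 for neutrophils, haemoglobin, platelets, creatinine or electrolytes. Protocol 1.4 names decreased neutrophil count among the important identified risks, and safety is the study's primary purpose.

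**Working it through.** No power or alpha calculation applies: SAP 4 and protocol 7.1 say that the 50 subjects were not chosen on statistical power. The check is a reading of every planned laboratory output, plus three simple counts.

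**1. How many analytes have a severity cut on the laboratory value itself?** Input: protocol Table 2, leaving out PSA and counting the white-cell differential as one row.
- Haematology 6 + biochemistry 13 = 19 rows.
- Several cuts (SAP 7.5.2.2): ALT and AST = 2.
- One cut (SAP 7.5.2.2): ALP and total bilirubin = 2.
- Reference range only: 19 - 2 - 2 = 15. These include haemoglobin, white cells and differential, platelets, creatinine, potassium, sodium, calcium and glucose.

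Not all 15 will have CTCAE numeric grades. The count says only that none has a planned severity cut.

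**2. What does the shift table show?**
- Normal at baseline, mildly low later: N to L.
- Normal at baseline, severely low later: N to L, the same cell.
- Mildly low at baseline, severely low later: L to L, no shift.

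The third subject is still counted as low; only the worsening is hidden. The same holds for H to H.

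**3. Do the other outputs give a count by worst grade?**
- *Graded adverse-event tables (SAP 7.5.1.2):* they give grade, but only for abnormalities that pass the protocol 5.5.1.1 judgement.
- *Grade 3+ events of special interest (SAP 7.5.1.3):* these cover neutrophils and platelets, but use reported adverse events and so inherit the same filter. Anaemia is not a category in SAP 6.2.
- *By-visit statistics, change from baseline and box plots:* these show the size of values but do not count subjects by severity. SAP 7.11.3 takes the value nearest the scheduled day within 7 days either side. After Day 85, visits are 84 days apart, so each window covers 7 + 1 + 7 = 15 days, and 15 / 84 = 17.9% of the interval. Routine samples should fall inside the window. An unscheduled sample, which the Schedule of Assessments allows, may not, and would then be left out of these statistics.
- *Spaghetti plots and listings:* individual extremes can be seen, but the reader has to grade and count them.
- *Liver table (SAP 7.5.2.2):* it uses worst values, but for four analytes only.

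For haematology and non-liver chemistry, no planned table gives a Grade 3-4 rate from the central-laboratory data.

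**4. How many subjects could be affected?** The documents give no share with low haemoglobin at baseline, so it is assumed: 0.20 x 50 = 10; 0.40 x 50 = 20; 0.60 x 50 = 30. These are subjects who could not show a fall in the shift table. How many would go on to Grade 3-4, or go unreported as an adverse event, cannot be estimated from the documents.

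**The case against.** The strongest objection is that the SAP does what the protocol asks. A reader might infer a contradiction, since protocol 5.5.4 applies CTCAE to abnormal laboratory values. The documents do not support that: the sentence sits in the section on adverse-event severity, while protocol 7.5.2, which governs the laboratory analysis, itself specifies shifts against normal ranges. This part of the objection stands in full.

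A reader might also infer that severity is reported nowhere, or that a severe cytopenia attributed to marrow disease would vanish from every table. That too goes further than the text. Protocol 5.5.1.1 brings disease-related findings back into reporting when they are worse than expected. Protocol 5.5.1.3 requires reporting where attribution to progression is uncertain or there is evidence of a causal link to study drug. A subject who falls from normal still shows as N to L, and one who stays low is still counted as low. ALT and AST are well covered by SAP 7.5.2.2, reported neutrophil and platelet events are graded, and with about 50 subjects the plots and listings will show large individual falls.

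These points narrow the gap but do not close it. Each route either depends on investigator judgement or leaves the grading and counting to the reader.

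**Conclusion.** The point holds as a reporting gap limited to haematology and non-liver chemistry: 15 of 19 analyte rows have no severity cut on the laboratory value, and the shift table cannot show same-direction worsening from an abnormal baseline. It is neither a departure from the protocol nor a total absence of severity information.

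The 10 to 30 subjects in the illustration rest on an assumed 20% to 60% with low haemoglobin at baseline. They should not be read as events missed. The structural point does not depend on that assumption, because it applies to any subject who starts out of range.

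The study is single-arm and descriptive, so no estimate of effect, test or decision rule changes. What would be gained is a rate of severe laboratory abnormality that does not depend on investigator attribution, for a primary endpoint and a named risk. That makes this a cheap and worthwhile improvement, not a flaw that undermines the study.

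**What to change.** Keep the L/N/H shift table, which meets protocol 7.5.2. Add to SAP 7.5.2.1, for analytes outside the liver table that have CTCAE v4.03 numeric grades:
- a shift from baseline grade to worst post-baseline grade, using all post-baseline values including unscheduled ones;
- the number and percentage of subjects newly at Grade 3 or higher.

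The candidates are haemoglobin, absolute neutrophil count, white cells, platelets, creatinine and electrolytes, with the list to be confirmed against the CTCAE text. Electrolytes that can deviate both ways should be tabulated separately for low and high. Protocol Table 2 lists only a white-cell differential without saying whether it is absolute or a percentage, so the SAP should state that the absolute neutrophil count is derived from white cells and differential where needed.

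The values are already collected through the central laboratory, so no new assessment is required. The cost is limited programming for a derivation and a table. If the SAP can no longer be changed before hard lock, the table can be added and justified in the clinical study report, as SAP 1 provides for changes to the planned analyses.
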